A methodologically rigorous SMART design will be used to test these adaptive interventions. Participants will be randomly assigned to one of the two initial treatment components: a) enhanced *physical activity monitor* only (physical activity monitor with goal setting and a physical activity prescription) treatment, or b) enhanced *physical activity monitor+motivational text messaging* treatment for 8 weeks (early adoption phase). Week 8 has been set as the decision point for women who have not met their physical activity step goal (i.e., non-responders). Non-responders will be those who a) fail to have valid wear time (i.e., wear a minimum of 3 days with 10 hours of wear time OR exceeding baseline step average), and b) average steps exceed the short-term goal of 600 steps above baseline average for two of the three weeks in weeks 6 to 8.. Non-responders to initial treatments will be randomly assigned to one of two augmented treatments: a) personal calls, or b) group meetings for Weeks 9-34 (later adoption phase). Responders will continue with their original treatment for Weeks 9-34 (later adoption). During Weeks 35-50 (maintenance), all women will receive enhanced physical activity monitors only. Data collection will occur at baseline and at Weeks 9-10 (end of early

adoption), 35-36 (end of later adoption), and 51-52 (end of maintenance). Data collection from the physical activity monitor (Fitbit Charge 2 or 3, hereafter referred to as Fitbit) will be ongoing and take place throughout the study.

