## VIII. Group Meeting Component

The group meeting treatment consists of five 45-60 minute group meetings held every four to six weeks during late adoption (Weeks 9-34). Due to the time needed to schedule, group meetings will start at Week 12. Group meetings will be led by a trained interventionist, held in a private conference room on the worksite property, and scheduled between the day and evening shift times. Participants will be able to attend in person or by using their own phones for

audioconferencing or Adobe Connect videoconferencing to interact and view group meeting materials. Technical support will be available to help navigate Webex.

The group meetings provide social support. The content for the first group meeting focuses on identifying realistic outcome expectations regarding the effects of physical activity, to ensure realistic short- and long-term goals. The second and third meetings address personal and environmental problems that can interfere with increasing physical activity. The fourth group meeting focuses on anticipating disincentives for physical activity and handling relapses. These group meetings are targeted to address participant's common barriers to physical activity, and identify benefits of physical activity. At the final group meeting, participants will share their experiences.

The group begins with a seven minute video of women role modeling (vicarious experience) by demonstrating skills, sharing experiences, and sharing approaches to problem solving and overcoming challenges pertinent to each group meeting. Following the video, each group meeting will include a 30-minute group discussion facilitated by the interventionist to role model, provide guidance, and encourage participants to solve problems together. A customized manual, including content for each group meeting, will be used to guide the discussion. At the conclusion of each discussion, participants will examine their step counts from the prior week in relation to their goal, identify a strategy for meeting the goal, and rate their self-efficacy (confidence) to meet the goal on a scale of 0-10. If their confidence is <8, the interventionist will recommend that participants reset their goal to one in which they have higher confidence. At the End of each group meeting, participants will complete a Group Meeting Satisfaction Tool (4 items assessing satisfaction with group meetings).

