Aim 2b. Aim 2b is to compare the four adaptive interventions in improving physical activity and cardiovascular health from baseline to 8, 34, and 50 weeks. The analysis is parallel to that described in Aim 1, except that the participants are not assigned to treatment based on simple randomization. Instead, they are screened on the basis of response status, and, once it has been ascertained that they did not respond to the initial treatment, they are randomly assigned to a treatment condition. Due to this design, the contrasts used to estimate the efficacy of these effects are nonorthogonal. The weights associated with the four interventions are then scored as a 4 for non-responder subgroups and 2 for responder subgroups. This is because responder subgroups are used twice in the design matrix (e.g., subgroup A is used in adaptive interventions 1 and 2; Figures 2 and 3). The estimation of these models is then based on a weighted multilevel linear regression model that has terms for change over time, the initial treatment, the augmented treatment, the interaction between the two treatments, and the effects of baseline and time-varying characteristics. The critical effect in this model is the time-by-adaptive-intervention interaction term. The null hypothesis is that there will be no interaction effect at all, while the alternative hypothesis is that adaptive intervention 4 (enhanced physical activity monitor+text messaging [initial] and enhanced physical activity monitor+text messaging with group meetings [augmented for non-responders]) will produce the largest improvement rates.

Aim 3. Aim 3 will identify mediators and moderators of the initial and augmented treatments on physical activity and cardiovascular health. Using analytic models parallel to those for Aims 1 and 2, we will first test impact on intervention targets (benefits, barriers, self-efficacy, social support).

Hypothesis: The intervention targets (benefits, barriers, self-efficacy, and social support) will mediate the effect of the initial and augmented treatments on physical activity (8, 34, and 50 weeks) and cardiovascular health (34 and 50 weeks).

Research Question: Do characteristics of participants (prior physical activity, demographics, BMI, depression) and their environment (walkability, crime) moderate the effects of the initial and augmented treatments on physical activity and cardiovascular health?

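### Aim 2b turns on a time-by-intervention interaction, but neither the coding of time nor the deciding contrast is defined; a straight-line coding would distort comparisons between interventions that share a first stage

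*SAP*

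**What the plan says.** Aim 2b (SAP; same text in Protocol section XII) is to "compare the four adaptive interventions in improving physical activity and cardiovascular health from baseline to 8, 34, and 50 weeks". The model is a "weighted multilevel linear regression model that has terms for change over time, the initial treatment, the augmented treatment", the interaction of the two treatments, and baseline and time-varying covariates. The SAP then states: "The critical effect in this model is the time-by-adaptive-intervention interaction term". The null is the complete absence of interaction. The alternative is that intervention 4 "will produce the largest improvement rates". The analysis is described as parallel to Aim 1, which says only that time is nested within participant.

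The documents give no coding for time, no knot, no equality constraint before week 8, and no contrast at a named week that decides the aim.

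The Protocol fixes when the interventions can differ:

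- Section I: "Week 8 has been set as the decision point for women who have not met their physical activity step goal". Interventions 1 and 2 share one first stage, and 3 and 4 share the other.
- Section VII places the personal calls in weeks 11-34. Section VIII says "group meetings will start at Week 12".
- Section I: "During Weeks 35-50 (maintenance), all women will receive enhanced physical activity monitors only".
- Outcomes are assessed at baseline and in weeks 9-10, 35-36 and 51-52 (section I).

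**The concern.** Within a pair that shares a first stage, no augmented treatment has been delivered by the week 9-10 visit. The true difference is therefore flat at zero, then builds to week 34, then is held or fades. A single slope per intervention cannot follow that shape. It spreads the difference over the whole year, so it shows a gap before one can exist, understates the gap at the end of treatment, and overstates it after withdrawal.

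Reading time as categorical removes that problem but leaves another. The interaction becomes a test with several degrees of freedom, and rejecting it does not say which intervention is best or when. If the choice is left until data are in hand, the coding of time can affect both significance and the ranking of the interventions.

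**Working it through.** **What can be reproduced.** The stated weights are inverse assignment probabilities: 1/(0.5 × 0.5) = 4 for non-responders and 1/0.5 = 2 for responders. The sample size of 312 cannot be reproduced, because no effect size, SD, response rate, dropout or power is given.

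**Inputs for the straight-line reading.** Visit times are t = 0, 9, 35 and 51 weeks (starts of the Protocol's windows). The true difference within a pair is 0, 0, d and r·d, where r is the share of the week-35 difference left at week 51. The documents do not give r, so it is assumed and varied from 0 to 1.

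**Fitted line (free intercept).** The mean of t is 23.75. The deviations are -23.75, -14.75, 11.25 and 27.25, and their sum of squares is 1650.75.

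- Slope = (11.25 + 27.25r)d / 1650.75 per week
- Fitted difference at t = (1 + r)d/4 + slope × (t - 23.75)

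For r = 0.5 the slope is 24.875/1650.75 = 0.01507d. At week 35 the line gives 0.375d + 0.01507d × 11.25 = 0.54d.

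| r | Week 9: fitted (true) | Week 35: fitted (true) | Week 51: fitted (true) |
|---|---|---|---|
| 0 | 0.15d (0) | 0.33d (d) | 0.44d (0) |
| 0.5 | 0.15d (0) | 0.54d (d) | 0.79d (0.5d) |
| 1 | 0.16d (0) | 0.76d (d) | 1.14d (d) |

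For any r the week-35 value is (0.327 + 0.436r)d, always below d. The week-51 value is (0.436 + 0.700r)d, always above r·d. Forcing a common intercept, with slope (35 + 51r)d/3907, gives 0.31d, 0.54d and 0.77d at week 35, so the conclusion does not depend on that choice.

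**Power.** Assume equal variances and equal correlations across visits. The noncentrality of the slope test, relative to the week-35 change from baseline, is √2 × (11.25 + 27.25r)/√1650.75. This is 0.39, 0.87 and 1.34 at r = 0, 0.5 and 1. It equals 1 at r = (√(1650.75/2) - 11.25)/27.25 = 0.64.

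**Simulation (illustrative).** It used 312 women, weights 4 and 2, replicated responders, cluster-robust standard errors, nominal weeks 0, 8, 34 and 50, and 1000 runs per setting. Assumptions were correlation 0.5, a non-responder difference of 0.5 SD, no dropout and two-sided 0.05. The contrast is the augmentation effect averaged over both first stages, so one pair alone would have less power.

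| Response rate | True week-34 difference (SD) | Slope test power, r = 1 / 0.5 / 0 | Week-34 change from baseline, power | Week-34 estimate, categorical time |
|---|---|---|---|---|
| 40% | 0.5 × 0.6 = 0.30 | 99% / 84% / 28% | 93-94% | 0.295-0.304 |
| 60% | 0.5 × 0.4 = 0.20 | 95% / 68% / 21% | 76-78% | 0.197-0.202 |

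**Categorical reading.** Four interventions by four occasions give an interaction with 3 × 3 = 9 degrees of freedom, or 7 if each pair is held equal through week 8. A text-messaging effect at week 8 that then vanished would make the null of no interaction false, even with no difference at week 34 or 50. That effect is already the subject of Aim 2a.

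**The case against.** The strongest reply is that the plan never says time is linear. The word linear describes the regression, not the time coding. Weeks 8, 34 and 50 are named as discrete occasions throughout, and an interaction among four interventions cannot be a single coefficient. All of this fits categorical time, under which the estimates are not distorted. The reply stands: a reader might infer from the reference to rates that the SAP commits to one slope per intervention, but that wording appears only in the alternative hypothesis and not in the model statement.

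Three other strong readings also go too far.

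- A reader might take all four interventions to be the same until week 8. Only 1 vs 2 and 3 vs 4 are, which is two of the six pairwise contrasts. Comparisons of 1 or 2 with 3 or 4 differ from the start through text messaging, so early divergence there can be real.
- A reader might equate dilution with lost power. Above about 64% persistence the slope test is the more powerful one.
- A reader might multiply the slope by 35 and report 0.24d, 0.53d and 0.82d. Those are changes implied by the slope alone. The fitted differences include the intercept and are 0.33d, 0.54d and 0.76d.

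For Aim 1 the case is weaker, since its text has no rate wording and names follow-up weeks. It is, however, the model that Aim 2b is said to parallel, and it too is silent on time coding.

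**Conclusion.** The point holds in conditional form and is worth acting on. Aim 2b does not define time or name a deciding contrast, and neither available reading gives a sound answer as it stands.

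- **Linear time:** for the two pairs that share a first stage, the week-35 difference is estimated at about 33% to 76% of its true value. A false difference of about 15% of d appears at week 9, and the week-51 difference is overstated at every persistence from 0 to 1. Power suffers only when the effect fades.
- **Categorical time:** no distortion, but the omnibus test can be rejected by the Aim 2a effect alone and does not identify the best intervention.

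The size rests on assumed persistence and on taking the visits at weeks 0, 9, 35 and 51. The power figures also rest on the assumed correlation, effect size, response rates and absence of dropout, and on applying the 0.05 level to Aim 2b, which the plan does not label as primary or secondary.

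**What to change.** In Aim 2b of the SAP, and in the matching text of Protocol section XII:

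1. Code time as a four-level factor, or as piecewise linear with knots at weeks 8 and 34. With four occasions at nominal weeks the two describe the same means.
2. Constrain interventions 1 = 2 and 3 = 4 through week 8.
3. Make the tests the intervention contrasts in change from baseline at week 34 and at week 50. Name one as deciding, or adjust the two for multiplicity.
4. Use the same time coding in Aim 1.

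The data and model class stay the same. The cost is a few more parameters (2 + 2 + 4 + 4 = 12 intervention-by-time means, against 4 intercepts and 4 slopes), two named tests in place of one, and some loss of power relative to a slope if the effect is largely maintained to week 50.

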- All participants will be thanked for their time, and will schedule their appointment for the next study visit in 9-10 weeks

*Decision Point 1: Week 8*

- This aspect of protocol procedures does not entail an in-person visit with the research team
- At week 8, the research team will remotely determine if participants are deemed responders or non-responders to their initial treatment assignment based on their daily Fitbit step count synced to iCardia at UIC. A participant is considered a *Responder* to the initial treatment if she meets both of the following criteria for two of the three weeks during weeks 6-8 of the initial intervention phase:
  - 1) Have 3 or more valid days, defined as either 10 hours of wear time or steps greater than baseline average steps, and
  - 2) Average at least 600 steps above baseline steps for the valid days.
- If she is deemed a responder, she will continue her initial treatment (physical activity monitor or physical activity monitor+text messages)
- If she is deemed a non-responder, she will continue her initial treatment (physical activity monitor or physical activity monitor+text messages) and, in addition, be randomly assigned to receive either of the two augmented treatment conditions
  - Personal calls
  - Group meetings
    - See section **IX. Randomization** for further details on the randomization process

*Data Collection Weeks 9-10 and Augmented Treatment Appointment (D2)*

- Participants will be notified of whether they have been deemed a responder or non-responder to their initial treatment, and, if deemed a non-responder, will receive the results of their second randomization
- Because of changes related to COVID-19, participants will complete the D questionnaire online using a secure REDCap survey link
- D2 data collection will include the following:
  - Questionnaires:
    - Exercise Benefits/Barriers Scale (Revised for PA)
    - McAuley's Self-Efficacy for Overcoming Barriers to PA
    - Social Support and Exercise (Revised for PA)
    - International Physical Activity Questionnaire (IPAQ) long-form
    - Sedentary Behavior
    - Emotional Distress-Depression Short Form 8b
    - PROMIS Scale v 1.2
    - PROMIS Sleep Impact Short Form
    - Outcome Realizations
      - 11 items measuring realized change due to becoming more physically active

- Program Orientation Satisfaction Tool
  - 7 items measuring satisfaction with the Program Orientation Process
- Fitbit Satisfaction Tool

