    - Participants will be asked about their best available times to meet, and the group leader (trained interventionist) will develop a schedule, based on the participants' collective input of best available times to meet, and will send it out to by Week 11 of the study to better ensure that enough group members are available for the meetings
- Participants will be thanked for their time, and will schedule their Data Collection Weeks 35-36 (D3) appointment

*Data Collection Weeks 35-36 Appointment (D3)*

- Because of changes related to COVID-19, participants will complete the D3 questionnaire online using a secure REDCap survey link
- D3 data collection will include the following:
  - Questionnaires:
    - Exercise Benefits/Barriers Scale (Revised for PA)
    - McAuley's Self-Efficacy for Overcoming Barriers to PA
    - Social Support and Exercise (Revised for PA)
    - Outcome Realizations
    - International Physical Activity Questionnaire (IPAQ) long-form
    - Sedentary Behavior
    - Emotional Distress-Depression Short Form 8b
    - PROMIS Scale v 1.2
    - PROMIS Sleep Impact Short Form
    - Fitbit Satisfaction Tool
    - Physical Activity Text Messaging Satisfaction Tool
    - For those in the Personal Call Condition only:
      - 13 items measuring satisfaction with receiving personal calls
    - For those in the Group Meetings Condition only:
      - 12 items measuring satisfaction with participating in the Group Visits
      - Social Provisions Scale
        - 24 items, 6 sub-scales each comprised of 4 questions scaled from 1 strongly disagree to 4 strongly agree reflecting:
          - Social provisions of attachment
          - Social integration
          - Reassurance of worth
          - Reliable alliance
          - Guidance
          - Opportunity for nurturance
  - Participants will be asked to come to the Physical Activity lab for a brief appointment to obtain:
    - Physical measures:
      - Three blood pressure readings, pulse, weight and waist circumference (a Physical Measures handout will be given to the participant that records these findings)
    - Fitness assessment:
      - Step fitness test
- The research team will give the participant a new step goal, based on their average daily step count (See **V. Physical Activity Goal** for more information about goal adjustment)
- For the third time in the study, participants will be given an Actigraph to wear for one week to assess their average daily steps

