Testing Adaptive Interventions to Improve Physical Activity for Sedentary Women

3/21/2018

NCT Number (not available yet)

Testing Adaptive Interventions to Improve Physical Activity for Sedentary Women

Statistical Analysis Plan

Under the direction of [name], SAS (v9.3) and R will be used for statistical analysis. Because multiple outcomes are being evaluated in the primary aim, a two-tailed .01 significance level will be used for the statistical tests of these hypotheses. Secondary and exploratory aims will employ a standard two-tailed significance level of .05 for all statistical tests. All analyses will be performed on an intent-to-treat basis. A one-way analysis of variance will be conducted to look for potential diffusion effects. If significant differences are found, the estimated mean levels of diffusion will be used as weights in the efficacy analyses and cost analysis. Hypothesis testing will address four study aims.

Aim 1. Aim 1 is to compare the two augmented treatments used for non-responders, personal calls and group meetings, in improving physical activity and cardiovascular health after 35 and 50 weeks.

Hypothesis: Group meetings will be more effective than personal calls in improving physical activity and cardiovascular health after 34 and 50 weeks, among non-responders to the initial treatment.

This hypothesis will be tested using a multilevel analysis with time nested within participant (i.e., non-responders only). The hypothesis of the study is that the non-responders who receive group meetings will demonstrate greater improvement in physical activity (self-report life-style and occupational physical activity: minutes of moderate/vigorous physical activity/weeks; device: number of steps/day, minutes of moderate/vigorous physical activity/ week) compared to those who receive personal calls.

Aim 2a. Aim 2a is to compare enhanced physical activity monitor with and without text messaging for improving the level of physical activity from baseline to 8 weeks. These analyses will parallel those used for Aim 1, but consider only two time points (baseline and 8 weeks) and include all participants.

Hypothesis: Participants who receive enhanced physical activity monitor+text messaging as compared to those who receive enhanced physical activity monitor alone will show greater improvement on physical activity at the end of 8 weeks.

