Although we will test the impact of each treatment on all potential intervention targets, we anticipate variation in impact by treatment (e.g., initial treatment is less likely to impact social support). For intervention targets that are significantly impacted by treatment condition, we will test whether they serve as mediators of intervention effects on physical activity and health status outcomes using methods described by MacKinnon. Moderation effects will be tested by adding moderator main effects and interactions of the moderators with condition and time. Significant moderator effects (i.e., significant moderator-by-time-by-treatment effects) will then be used to identify optimal decision rules for individual participants. The estimation of optimal decision rules will be achieved using a Q-Learning analysis, which is a modified regression analysis, adapted to address the SMART design. These optimal decision rules can then be cross-validated in future studies.

Aim 4. The cost-effectiveness analysis will be conducted from the societal perspective, including the program and participant costs. For the cost measurement, quantities of resources used and their associated prices will be collected for the program (either amounts paid or the value of the interventionist's time), and participant (i.e., the value of the participant's time to participate in the program). All costs will be valued in 2017 dollars. Program costs and participant costs will be calculated by summing their respective individual cost components, and these costs will be summed to calculate the total cost per participant.

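### Aim 3's mediation tests for the initial treatment at Week 8 and the augmented treatment at Week 34 take the target from the same assessment wave as the outcome, so they cannot tell a driver of activity from a result of it

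*SAP*

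**What the plan says.** The SAP (Aim 3, repeated in Protocol XII) states that the four intervention targets "will mediate the effect of the initial and augmented treatments on physical activity (8, 34, and 50 weeks"), and on cardiovascular health at 34 and 50 weeks only. The procedure has two steps. The first is: "Using analytic models parallel to those for Aims 1 and 2, we will first test impact on intervention targets". For targets that treatment significantly affects, the second is: "we will test whether they serve as mediators of intervention effects on physical activity and health status outcomes using methods described by MacKinnon". No target wave, lag or adjustment for earlier activity is named. The Week-8 model that Aim 3 parallels (Aim 2a) will "consider only two time points (baseline and 8 weeks) and include all participants".

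On timing, Protocol I says "Data collection will occur at baseline and at Weeks 9-10 (end of early" adoption), followed by Weeks 35-36 and 51-52. Protocol IV places the target scales in the D1, D2, D3 and D4 questionnaires and nowhere else.

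**The concern.** A mediation claim says that treatment moved the target and the target then moved activity. If target and activity are first observed after treatment in the same wave, the opposite order fits equally well: treatment moved activity, and being more active raised confidence or lowered perceived barriers.

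The protocol's own rationale makes that reverse path plausible. Protocol V sets gradual step goals in order to build self-efficacy, and the Fitbit signals each goal reached. Protocol VI tells the text-message arm its step classification every week. Protocol IV also lists notification of responder status under D2, whereas Protocol XI puts it after the Actigraph is returned. If the former is followed, some women may rate self-efficacy after learning whether they succeeded.

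At stake is the mechanism conclusion. Aim 3 promises to identify mediators, and later programs could be built around a target that is only a by-product of walking more.

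**Working it through.** The documents give no power, effect-size or non-response figure for Aim 3, so there is no planned figure to reproduce. The check has two parts.

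**1. Schedule against hypothesis** (Protocol I, IV, VII, VIII, XI)

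| Treatment and outcome time | First target value that can reflect treatment | Outcome wave | Earlier-wave target available? |
|---|---|---|---|
| Initial, Week 8 | D2 (Weeks 9-10) | D2 | No |
| Initial, Week 34 | D2 | D3 (Weeks 35-36) | Yes |
| Initial, Week 50 | D2 | D4 (Weeks 51-52) | Yes |
| Augmented, Week 34 | D3 | D3 | No |
| Augmented, Week 50 | D3 | D4 | Yes |

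D2 cannot serve for the augmented treatment: women are notified after D2, calls run in Weeks 11-34 and groups start at Week 12. The 0-10 confidence rating in Protocol VIII is described for group meetings only, so it cannot support a comparison with calls.

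Within a wave, self-reported activity (IPAQ) is in the same online questionnaire as the targets. The Actigraph is handed out at the lab appointment and worn for the following week. Fitbit Weeks 6-8 precede D2. The documents do not say which device window is the Week-8 outcome.

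**2. Size of the error if the target is only a consequence**

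Inputs from the documents: 312 women (Protocol I), 1:1 allocation (Protocol XI), hence 156 per arm; two-sided .05 for secondary aims (SAP).

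Assumed:
- non-response of 50% (0.50 × 312 = 156, or 78 per arm) or 30% (0.30 × 312 = 93.6, about 94, or 47 per arm);
- treatment effect on activity d = 0.3-0.5 SD;
- standardized activity-to-target slope g = 0.3-0.5;
- stability 0.5;
- no effect of target on activity.

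The test is joint significance of treatment on target and of target on activity, both adjusted for baseline target and activity. This mirrors the SAP's two steps. In this model:
- the treatment effect on the target is g × d;
- the residual variance of the target is 1 − 0.5² = 0.75, so SE = √(0.75 × 2/n per arm);
- the partial correlation of target and activity is g, so the second test has t ≈ g√(N − 5)/√(1 − g²).

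Example with 156 per arm and d = g = 0.5: SE = √(1.5/156) = 0.098; z = 0.25/0.098 = 2.55; P(significant) = Φ(2.55 − 1.96) = 0.72. The second test has t ≈ 0.5 × √307/√0.75 = 10.1 and nearly always passes. Simulation (2,000 trials) gave 73%.

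Simulated rate of falsely declared mediation:

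| Per arm | d=.3, g=.3 | d=.3, g=.5 | d=.5, g=.3 | d=.5, g=.5 |
|---|---|---|---|---|
| 156 | 15% | 33% | 34% | 73% |
| 78 | 10% | 20% | 19% | 42% |
| 47 | 7% | 13% | 12% | 27% |

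- With g = 0 the rate is at most 0.4%. With d = 0 and g > 0 it is about 4-5%.
- Without baseline adjustment (4,000 trials), the ranges are 13-61% at n=312 and 9-35% at n=156. A third specification gave 17-74% (n=312), 12-44% (n=156) and 7-29% (n=94). The envelope is 13-74% at n=312 and 7-44% at n=94-156.
- Lagging alone does not help. A target taken one wave before the outcome, without adjustment for activity at the target's wave, still gives 73% at 156 per arm with d = g = 0.5. With that adjustment the rate is 3.4% there, and at most 5% in every cell run, including d = 0.8.

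These rates are for one target and one outcome; the plan tests four targets.

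**The case against.** Several points on the other side stand.

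- A reader might infer that a consequence of activity *will* be reported as a mediator. That is not shown. It needs a treatment effect on activity and an effect of activity on the target, and both are assumed here. For the augmented comparison, 0.3-0.5 SD would be a difference between two active treatments.
- A reader might also infer that target and outcome always come from one visit, with the target measured with or after the outcome. That is too strong. The questionnaires are online, and body measures and the step test come from a separate lab appointment. The Actigraph week, which can supply the device outcomes, follows that appointment. Same wave is accurate. A gap of days after weeks of treatment gives only weak ordering.
- The cited mediation methods cannot be seen from the documents. Where ordered data exist (initial treatment at Weeks 34 and 50, augmented treatment at Week 50), the plan is unspecified and not shown to be wrong. For the other two effects, no method can supply an order that was not measured.
- The adjusted lagged model has a cost. It removes the part of true mediation already completed by the target's wave. The simulation assumed true mediation with treatment-to-target effects of 0.3-0.5 SD, target-to-activity slopes of 0.3-0.5 and target stability of 0.3-0.6. The lagged model detected it in 10-88% of trials at n=156, against 47-97% for the same-wave model; at n=312 the figures were 29-99.9% against 77-100%. A separate run gave 27-71% against 57-96% at n=156.

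This last point argues against discarding the same-wave analysis, but it does not make that analysis directional.

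**Conclusion.** The concern holds for two of the effects Aim 3 names: the initial treatment at Week 8 and the augmented treatment at Week 34. That rests on the measurement schedule alone. For these, the data can show that a target and activity move together under treatment, but not which moves the other.

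The size depends on assumptions. Under pure reverse causation with the stated values, a same-wave test declares mediation in roughly 13-74% of trials at n=312 and 7-44% at n=94-156. The non-responder numbers, effect sizes and slopes are not in the documents. The documents do not support the wider reading that all of Aim 3's mediation analysis is invalid, since ordered pairs are already scheduled; the plan just does not commit to using them. As a secondary aim, this should be corrected but does not touch the primary comparison.

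**What to change.** Amend the Aim 3 wording in the SAP and the matching text in Protocol XII:

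1. Name the target wave for each mediation test, and the device window that defines the Week-8 outcome.
2. Report the initial-treatment Week-8 and augmented-treatment Week-34 results as non-directional associations, not as identified mediators.
3. Base directional claims on ordered pairs. For the initial treatment, use the D2 target with the Week-34 or Week-50 outcome, accounting for response status and second assignment, because augmentation follows from response and can change later targets and outcomes. For the augmented treatment (non-responders only), use the D3 target with the Week-50 outcome. In each, adjust for the earlier target value and for activity at the target's own wave.
4. Add a sensitivity analysis for reverse causation and for target-outcome confounding, which ordering does not remove.

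No new visit or measure is needed. The downsides should be stated in the SAP. There is no directional claim for the 8-week effect or for the augmented 34-week effect, which is an Aim 1 time point. Power to detect true mediation is lower in the adjusted lagged model. The D3-to-Week-50 pair spans Weeks 35-50, when all women have monitors only, so it addresses maintenance after augmentation has ended, which is a different question.
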